7.3.1.1 Classifications

Severity

The Investigator will evaluate the severity of each adverse event using the following definitions:

Mild - Transient symptoms, no interference with the subject's activities of daily living

Moderate – Marked symptoms, moderate interference with the subject's activities of daily living

Severe – Considerable interference with the subject's activities of daily living

In the event of the occurrence of a severe adverse event, the Investigator will be instructed to immediately inform the medical monitor.

An AE that has been assessed as severe should not be confused with an SAE. Severity is a category utilized for rating the intensity of an event; and both AEs and SAEs can be assessed as severe. An event should be described as 'serious' when it meets one of the pre-defined outcomes as described in Section 7.3.1.

Toxicity Grade

The Investigator will also provide AE severity grading per CTCAE (Version 5.0)

Causality

The Investigator is obligated to assess the relationship between test drug and the occurrence of each AE/SAE. The Investigator will use clinical judgment to determine if there is a reasonable possibility that the pharmacological action of the test drug was responsible for the AE/SAE being reported. Alternative causes such as natural history of the underlying diseases, concomitant therapy, other risk factors, and the temporal relationship of the event to the test drug will be considered and investigated. The Investigator will also consult the Clinical Investigator's Brochure and/or Product Information, for marketed products, in the determination of his/her assessment.

After careful medical consideration, the Investigator will evaluate the relationship of each adverse event to test drug applying the following definitions:

Probably Related – Good reasons and sufficient documentation to assume a causal relationship

Possibly related – A causal relationship is conceivable

Unlikely related – The event is most likely related to etiology other than the test drug

Not Related – Good reasons and sufficient documentation to exclude a causal relationship.

There may be situations when an SAE has occurred and the Investigator has minimal information to include in the initial report. However, it is very important that the Investigator always assess causality for every event prior to transmission of the SAE Report Form to the Sponsor (or designee).

7.3.2 Adverse Event Reporting

All events that meet the definition of an AE and occur in the period from when the subject has signed the informed consent form (ICF) through trial completion (final visit), or early termination, must be recorded on the adverse event CRF. All SAEs will be recorded on the appropriate CRF and on the Serious Adverse Event Report Form from the time written informed consent has been obtained through trial completion (final visit), or early termination.

At each contact between the investigative site and the subject (visit or phone), after the subject has had an opportunity to spontaneously mention any problems, the Investigator should inquire about the occurrence of AEs. The following are examples of open-ended questions that may be used to obtain this information:

“How are you feeling?”

“Have you had any medical problems since your last visit/assessment?”

“Have you taken any new medicines, other than those given to you in this study, since your last visit/assessment?”

All AEs and SAEs will be documented in source records at each assessment time or when otherwise volunteered by the subject and recorded on the appropriate CRF. Information to be collected includes the nature, date and time of onset, severity, duration, relationship to test drug, and outcome of the event. Even if the Investigator assesses the AE as not reasonably attributable to the test drug, its occurrence must be recorded in the source documents and reported on the CRF along with the assessment of association.

The Investigator will treat the subject as medically required, and this may extend beyond the duration of the trial. The Investigator will record treatment and medications required to treat AEs on the appropriate CRF(s). All SAEs, and any possibly/probably related severe AEs will be followed until resolution. Resolution of an AE is defined as that point in time when no further changes in the event are expected, that is, the point at which a subject experiencing such an AE is appropriately treated and stabilized even though they may continue to experience lingering sequelae that may never resolve.

DURECT’s designee will evaluate all AEs with respect to seriousness, causality and expectedness in accordance with Directive 2001/20/EC (3) and FDA Guidelines. The expectedness of an AE will be determined according to the current version of the Investigators Brochure.

7.3.3 Reporting of Serious Adverse Events

Regardless of causality, the investigator must complete and submit an SAE report form to PPD/CCI within 24 hours of knowledge of the event for all serious adverse events.

Submit SAE Report Forms via facsimile or email to:

PPD/CCI
[REDACTED]
[REDACTED]
[REDACTED]

The Investigator must indicate the SAE's relationship to test drug and sign the SAE report form. When additional relevant information (final diagnosis, outcome, results of specific investigations, etc.) becomes available, the investigator must record that follow-up information in the eCRF. Follow-up information should be recorded according to the process used for reporting the initial event as described above. The investigator will follow all reportable events (i.e., SAEs) until resolution. Resolution means no further changes in the event would be expected, i.e., the point at which a subject experiencing such an AE is appropriately treated and stabilized even though they may continue to experience lingering non-serious sequelae that may never resolve.

PPD/CCI [REDACTED] will follow all SAEs until resolution (See Section 7.3.2). PPD/CCI [REDACTED] will report all SAEs to DURECT within 1 business day of receipt.

All serious adverse events will also be reported on the AE CRF and concomitant medications administered in association with the serious AE will be documented on the CM CRF.

If a serious adverse event occurs and comes to the attention of the Investigator after trial completion/termination within 30 days of test drug dosing or within 30 days of the last trial visit (whichever occurs later), it must be reported immediately to PPD/CCI [REDACTED] in the same manner as the serious adverse events occurring during the trial. Investigators are not obligated to actively seek AEs from former study participants.

The Investigator must report SAEs to the IRB/IEC (per the IRB/IEC guidelines/SOPs), including all SAEs that have occurred at the investigative site and all trial related SAEs that have resulted in an expedited safety report to a regulatory agency. Concurrently, the Investigator must send DURECT documentation of such IRB/IEC notification or if reporting is not required immediately per IRB/IEC guidelines, then a copy of the local SOP stating the reporting guidelines should be supplied by the site to DURECT and the CRO.

DURECT complies with applicable regulatory requirement(s) related to the reporting of SUSARs to the competent authorities and the IRBs/IECs. In addition, DURECT will prepare annual safety reports covering all SUSARs that have occurred in clinical studies with the concerned test drug during the reporting period.

7.3.4 Adverse Event Follow-up

During and after participation by a subject in a clinical trial, the Investigator will ensure that adequate medical care has been provided to the subject for any AEs including clinically significant laboratory values related to the trial. The Investigator will inform the subject when medical care will be needed for intercurrent illness (es) of which Investigator becomes aware.

All SAEs and possibly/probably related severe AEs must be followed by the Investigator until resolution (See Section 7.3.2), until the subject is lost to follow-up, or died and until all queries related to the AEs have been resolved.

If a subject dies during participation in the study or during a recognized follow-up period, the Sponsor (or designee) must be notified immediately and then provided with a copy of any post-mortem findings, including autopsy and histopathology.

7.4 Pregnancy

Pregnancy tests will be done at screening visit and on Day 28 for females of child-bearing potential

Female subjects will be advised to notify the Investigator immediately if they become pregnant during the course of the trial.

The Investigator must complete the appropriate pregnancy reporting forms and send them to DURECT (or DURECT's designee) within 14 calendar days of obtaining information of the pregnancy. The Investigator will follow the pregnancy through its course and complete the appropriate documentation and forward immediately to DURECT (or DURECT's designee). The infant must be followed at least until one month of age. Consent of a parent must be obtained before registration of infant data.

Abortion, stillbirth and any malformation/disease must be reported as an SAE. A pregnancy outcome other than abortion, stillbirth and any malformation/disease as well as follow-up of the infant must be reported by the Investigator within 14 calendar days of obtaining the information using the appropriate pregnancy reporting forms.

8.0 PHARMACOKINETICS

Plasma samples will be collected from each of the first 10 patients enrolled. These samples will be used to calculate relevant pharmacokinetic parameters of DUR-928 determined using standard non-compartmental method with linear/log-trapezoidal rule utilizing an appropriate pharmacokinetic data analysis program.

Pharmacokinetic parameters, such as C_{max} , T_{max} , $T_{1/2}$, AUC_{0-last} , AUC_{inf} , CL , and V_d , for DUR-928 will be calculated and summarized by dose group and Part A or B using descriptive statistics.

Additionally, if appropriate, PK/PD analysis will be undertaken. MELD score, serum chemistry, and/or biomarker(s) may be used as PD variables for PK/PD analysis.

PK Sample Timepoints:

PPD/CCI

Sites will have flexibility to collect PK samples around e [PPD/CCI].
The time window for [PPD/CCI] time point PK sample collection can be [PPD/CCI].
The [PPD/CCI] post-dose initiation sample should be collected [PPD/CCI], as close as possible, since it is the highest drug concentration (Cmax) time point. The [PPD/CCI] sample can be collected within [PPD/CCI] of post-dose initiation timeframe. All samples must be clearly labeled with the actual date and time of collection. A total of up to [PPD/CCI] will be collected and processed for plasma. Plasma samples should be stored at -80 C until analysis.

See [PPD/CCI] for collection, storage, and shipment of samples.

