3.11.4 Dosage and Regimen

Assigned study treatment (DUR-928 or placebo) will be administered on Day 1 and on Day 4 in PPD/CCI [REDACTED] by intravenous infusion over approximately 2 hours PPD/CCI [REDACTED] until entire dose is given.

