5.2.2 Day 1 (In-hospital, Study Treatment)

The following procedures will be performed pre-dose unless otherwise noted:

- Review of inclusion / exclusion criteria to confirm eligibility
- Vital signs (BP, HR, respiratory rate, oxygen saturation, and temperature) pre-dose
- Physical exam (including weight) when feasible
- PPD/CCI 
- Safety labs (chemistry, hematology, urinalysis, coagulation) at pre-dose
 - NOTE: If a subject is screened and dosed on the same day, only the safety labs for Screening should be collected. An additional collection for Day 1 Pre-dose safety labs does **not** need to be performed.
- 12-lead ECG (post-dose completion/end of infusion)
- Adverse events and concomitant medications
- Biomarker samples collection (blood) at pre-dose when feasible
- Randomization

- Study Drug Dosing

5.2.3 Day 2

- Vital signs (BP, HR, respiratory rate, oxygen saturation, and temperature)
- Physical exam (including weight) when feasible
- PPD/CCI [REDACTED]
- Safety labs (chemistry, hematology, urinalysis, coagulation)
- Biomarker samples collection (blood) when feasible
- 12-lead ECG (when feasible)
- Adverse events and Concomitant medications

5.2.4 Day 3

- Vital signs (BP, HR, respiratory rate, oxygen saturation, and temperature)
- Physical exam (including weight) when feasible
- Safety labs (chemistry, hematology, urinalysis, coagulation)
- Biomarker samples collection (blood) when feasible
- 12-lead ECG (when feasible)
- Adverse events and concomitant medications

5.2.5 Day 4

- Vital signs (BP, HR, respiratory rate, oxygen saturation, and temperature) pre-dose
- Physical exam (including weight) when feasible
- Safety Labs (chemistry, hematology, urinalysis, coagulation) pre-dose
- 12-lead ECG (post-dose completion/end of infusion)
- Adverse events and Concomitant medications
- Biomarker samples collection (blood) at pre-dose when feasible
- PPD/CCI [REDACTED]
- Study drug dosing (Dose 2 of assigned study drug)

5.2.6 Day 5 and Day 6

Subjects will not be kept in the hospital longer than is medically required. If subjects remain hospitalized on Day 5 and Day 6, the following procedures will be performed and, *regardless*

of hospitalization, occurrence of AEs, and intake of concomitant medications will be assessed (in person or via phone contact):

- Vital signs (BP, HR, respiratory rate, oxygen saturation, and temperature)
- Physical exam (including weight) when feasible
- Safety labs (chemistry, hematology, urinalysis, coagulation)

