7.2 Method and Timing of Assessments

Safety will be evaluated using serious adverse events, vital signs, clinical laboratory tests and electrocardiograms. Refer to [Table 1](#) for the frequency and timing of assessments.

Where time-points of different measurements and/or blood samples coincide, the following sequence applies:

1. Vital Signs

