2. ECG
3. Safety labs
4. Biomarkers (blood)
5. Pharmacokinetic sample collection

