7.2.2 Spontaneously Reported Adverse Events

Spontaneously reported AEs; either volunteered by the subject, prompted by non-directed questioning or reported by an investigator will be documented on the CRF.

7.2.3 12-Lead ECGs

Standard resting 12-lead ECGs will be obtained after subject is resting in the supine position for 10 minutes at the time points listed in [Table 1](#). Additional ECGs may be obtained if clinically indicated.

Overall interpretation and machine read intervals (HR, PR, QRS, QT, and QTc) will be recorded on the ECG eCRF. Clinically significant ECG findings, per the Investigator's clinical judgment, that emerge after treatment will be recorded on the AE CRF.

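### The assessment order in Sections 7.2 and 7.2.5 pulls against Section 8's tight timing for the Cmax sample; if the draw shares its time point with the end-of-infusion ECG, observed Cmax can be lowered

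*Combined protocol and SAP*

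**What the plan says.** Section 7.2 sets a general order: "Where time-points of different measurements and/or blood samples coincide, the following sequence applies". The list runs from vital signs through ECG, safety labs and biomarkers to "5. Pharmacokinetic sample collection". It states no exception. Section 7.2.5 adds, without any condition about coinciding times, that vital signs come before blood is taken.

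On both dosing days (Sections 5.2.2 and 5.2.5) the ECG entry reads "12-lead ECG (post-dose completion/end of infusion"). Section 7.2.3 adds that "Standard resting 12-lead ECGs will be obtained after subject is resting in the supine position for 10 minutes". Study treatment is given "by intravenous infusion over approximately 2 hours" (Section 3.11.4).

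Section 8.0 gives sites some flexibility on sampling but singles out one sample, to be collected "as close as possible, since it is the highest drug concentration (Cmax) time point". It also requires the actual collection date and time on every sample. The nominal sampling times, the windows, the words just before that phrase and Table 1 are redacted.

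**The concern.** Under a constant-rate infusion with ordinary elimination, concentration is highest when the infusion stops and falls from then on. If the Cmax sample is meant for that moment, anything that must be done first moves the draw onto the falling part of the curve. In a non-compartmental analysis Cmax is simply the highest observed value, so a late draw can only lower it. Recording the true draw time does not bring the peak back.

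Cmax is a named parameter in Section 8, and Section 11.5 has the DMC review early pharmacokinetic data alongside safety. According to the synopsis, up to 4 samples are taken, after only one of the two doses, so no second dosing occasion is planned on which to recover a missed peak. Sites that follow Section 7.2 and sites that put Section 8 first would also differ systematically, in a very small sample.

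**Working it through.** The plan gives no half-life, expected Cmax or tolerated error in its readable text, so there is no figure to reproduce. The check has three parts.

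**1. Which items can come before the draw.** On Days 1 and 4, vital signs, safety labs and biomarkers are listed as pre-dose; for Day 4 the labs entry is "Safety Labs (chemistry, hematology, urinalysis, coagulation) pre-dose". They do not share an end-of-infusion time point. The ECG does, and it stands ahead of the pharmacokinetic draw in the Section 7.2 list. Section 7.2.5 could bring in a further set of vital signs, because its wording is unconditional, although a site could also take the pre-dose set as satisfying it.

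**2. Size of the shortfall.** Assume mono-exponential decline once the infusion stops:

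shortfall in observed Cmax = 1 − 0.5^(delay / half-life)

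Both inputs are assumptions. A delay of 10 minutes represents the full supine rest taken after the infusion. A delay of 5 minutes represents rest completed during the infusion, so that only the ECG recording comes first.

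| Assumed half-life | No delay | 5 min | 10 min |
|---|---|---|---|
| 0.5 h | 0% | 10.9% | 20.6% |
| 1 h | 0% | 5.6% | 10.9% |
| 2 h | 0% | 2.8% | 5.6% |
| 4 h | 0% | 1.4% | 2.8% |

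The two ends of the range are:
- 10 min at 0.5 h: 1 − 0.5^(10/30) = 20.6%.
- 5 min at 4 h: 1 − 0.5^(5/240) = 1.4%.

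**3. How many subjects are involved.** Sampling is in the first 10 enrolled. With 3:1 allocation, 10 × 0.75 = 7.5 are expected on DUR-928, so about 7 or 8.

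**The case against.** The strongest reply is that the coincidence is not shown. The Section 7.2 order applies only when time points coincide, and the sampling times are redacted. What can be read times the Cmax sample from the start of dosing and the ECG from its completion, and the infusion lasts only approximately 2 hours. The blacked-out words might even settle the priority. This stands as a limit on certainty. It does not remove the point, because a sample labelled as the peak of an infusion of about 2 hours very probably belongs at its end.

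Next, Section 8 is specific to this sample, and a careful site may let it override the general order. That is possible, but no readable passage says so.

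Third, Section 7.2.3 does not say that the 10-minute rest begins when the infusion stops. A hospitalised subject can rest supine during the infusion. This stands, and it is why the 5-minute column is shown.

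A reader might infer several stronger things that the documents do not support:
- **That Cmax is biased low.** This needs a coinciding time point, a real delay and a half-life that is short relative to that delay. None of these can be read from the plan.
- **That the loss could be well above 21%.** This needs longer delays or shorter half-lives than those assumed here, and the documents give no basis for either.
- **That AUC is distorted to the same degree.** Actual draw times are recorded, so AUC and half-life are less affected than Cmax.

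**Conclusion.** The conflict in the text is real: Sections 7.2 and 7.2.5 pull one way and Section 8 the other, with no readable rule of priority. The consequence is conditional. If the Cmax sample and the dosing-day ECG share the end-of-infusion time point, and a site follows the general order, observed Cmax can be lowered by about 1% to 21%. That range rests on an assumed delay of 5 to 10 minutes, assumed half-lives of 4 h down to 0.5 h and mono-exponential decline. With a prompt draw the effect is near zero. The direction is certain once there is a delay after the infusion stops; the size cannot be fixed from the documents.

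The reach is modest. Pharmacokinetic results are descriptive, come from few treated subjects and do not enter the primary endpoint, and no readable decision rule uses a Cmax threshold. What is exposed is the pharmacokinetic summary and the DMC's review of it. The point is worth acting on because the correction is cheap and can only remove a downward error.

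**What to change.** Add the same sentence to Sections 7.2, 7.2.5 and 8: where the Cmax sample coincides with other assessments, it is drawn first, at its nominal time, and the ECG and any vital signs follow immediately.

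State in Section 8 that parameters are calculated from actual draw times relative to the actual infusion start and stop times, and make sure that both infusion times are captured. Collection times are already required on each sample.

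The cost is a short text change in three places and a note in the sampling instructions, with no added procedure. The downside is that the dosing-day ECG is taken a few minutes later and after a blood draw.

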9.0 STATISTICAL METHODS AND DATA ANALYSIS

9.1 Research hypotheses

While this trial will provide important exploratory analyses of efficacy, particular attention will be given to the pre-specified primary endpoint and to the pre-specified secondary endpoints.

The primary endpoint is the composite of being alive and free of acute lung, liver or kidney organ failure at day 28.

- [PPD/CCI]

9.2 Sample Size Determination

A Pearson chi-square statistic will be used to compare the proportion of responders between treatment groups for the primary endpoint, ‘alive and free of acute lung, liver or kidney organ failure at day 28’.

[PPD/CCI]

Eighty subjects will be enrolled in this study and will be randomized to receive DUR-928 or placebo in a 3:1 ratio.

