3.8 CURRENT TRIAL

3.9 Trial Objectives and Primary Endpoints

Primary:

- Evaluate safety in subjects treated with DUR-928 as evidenced by treatment-emergent serious adverse events (TESAEs), including
 1. Respiratory failure events

- 2. Liver failure events
 - 3. Renal failure events
 - 4. Heart failure events
 - 5. Secondary infection (regardless viral or non-viral)
- Evaluate efficacy of DUR-928 in treatment of acute organ failure, especially acute liver or kidney injury, in subjects infected with SARS- CoV-2. The primary efficacy endpoint is the composite of being alive and free of acute organ failure at Day 28. This is specifically defined as being:
 - Alive at Day 28
 - Free of mechanical ventilation at Day 28
 - Free of acute liver failure (i.e., free of the simultaneous presence of: jaundice, coagulopathy, ascites, and hepatic encephalopathy) at Day 28
 - Free of renal replacement therapy at Day 28

Secondary:

- Alive at Days 28 and 60
- Alive, out of ICU, at Day 28
- Alive, out of hospital, at Days 28 and 60

PPD/CCI

[Redacted text block containing multiple lines of blacked-out content]

¶ [REDACTED]

¶ [REDACTED]

¶ [REDACTED]

¶ [REDACTED]

¶ [REDACTED]

¶ [REDACTED]

¶ [REDACTED]

¶ [REDACTED]

¶ [REDACTED]

¶ [REDACTED]

¶ [REDACTED]

¶ [REDACTED]

¶ [REDACTED]

¶ [REDACTED]

¶ [REDACTED]

¶ [REDACTED]

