3.11.1 Inclusion Criteria

To participate in this study, subjects must meet all of the following criteria:

1. Age 18-80 years old and able to provide written informed consent (either from subject or subject's legally acceptable representative)
2. Hospitalized with documented COVID-19 infection diagnosed by standard RT-PCR or equivalent testing other than anti-COVID-19 antibody testing (either upon entry into the hospital, in the hospital, upon admission to the ICU, or in the ICU)
3. Hospitalized with moderate, severe, or early critical COVID-19 illness:
 - c. Mean arterial pressure (MAP) \geq 60 mm Hg, including patients who require no more than one intravenous pressor at the time of enrollment;
 - d. If the subject is on ventilator at the time of Day 1 dosing, the total days on ventilator should be $<$ 5 days ($<$ 120 hours).
4. Subject meets one (lung only) or two (lung with liver or kidney) of the following criteria at the time of enrollment:
 - a. Acute liver injury irrespective of known, suspected, or unknown hepatic fibrosis or cirrhosis:
 - In subjects without a known history of liver disease and/or with a documented normal ALT level within past 12 months, acute liver injury will be defined as ALT $>$ 2x ULN and bilirubin $<$ 2.5.

- In subjects with a known abnormal baseline ALT level within past 12 months, acute liver injury will be defined as ALT >2x baseline level and bilirubin <2.5.
- b. AKI:
- Creatinine increase ≥ 0.3 mg/dL (26.52 $\mu\text{mol/L}$) in 48 hours or increase ≥ 1.5 times baseline within the prior 7 days
- c. Severe COVID-19 pneumonia defined by the following:
- Severe bilateral diffuse infiltrates & ground glass opacities involving more than 50% of the lung fields
- OR
- PaO₂ to FiO₂ ratio 100 to 300.
5. Women of child-bearing potential (defined as women gender assigned at birth) who are not surgically sterile or who are not over the age of 52 and amenorrhoeic for at least 12 months) must utilize appropriate birth control throughout the study duration. Acceptable methods that may be used are abstinence, birth control pills (“The Pill”) or patch, diaphragm, IUD (coil), vaginal ring, condom, surgical sterilization or progestin implant or injection, or sexual activity limited to a sterile (e.g., vasectomized) male partner.
6. Male subjects must agree to use a medically acceptable method of contraception/birth control and refrain from sperm donation throughout the study duration

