3.11.2 Exclusion Criteria

To participate in this study, subjects must NOT meet any of the following exclusion criteria:

1. Critical COVID-19 illness:
 - MAP < 60 mm Hg
 - On mechanical ventilator for ≥ 5 days
2. On maintenance (chronic) hemodialysis or peritoneal dialysis
3. History of end stage renal disease (ESRD) or CKD with eGFR < 15 mL/min/1.73 m²
4. Child Pugh C cirrhosis or cirrhosis with any decompensation event (ascites, hydrothorax, hepatic encephalopathy, or clinically significant variceal bleed) within the past 3 months.
5. The presence of acute liver AND kidney injury defined as meeting criteria for AKI in the presence of ALT >1.5x ULN and bilirubin >1.5 mg/dL
6. Participant of other clinical trials
7. Receipt of other concomitant experimental therapies except antiviral drugs
8. Underlying diseases that, in the opinion of the principal investigator, might be complicated or exacerbated by proposed treatments or might confound assessment of study drug

9. Any active malignancies other than skin cancer (basal cell carcinoma) amenable to local curative therapy. Patients with other potentially curable malignancies that have been treated and are in remission for at least five years shall be eligible for enrollment in the study.
10. Women who are pregnant or breast feeding

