5.1 Trial Test Drug

5.1.1 Randomization

Subjects will be assigned randomly at a 3:1 ratio to the following treatment groups:

- **DUR-928**, 150 mg in PPD/CCI [REDACTED] administered over approximately 2 hours via IV infusion.
- **Sterile Water for Injection**, 5mL (placebo) in PPD/CCI [REDACTED] administered over approximately 2 hours via IV infusion

More details on preparation and administration of study drug will be provided in the Pharmacy Manual for this study.

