9.3 Subject Randomization

A total of 80 subjects will be enrolled into the following 2 study treatment groups in a 3:1 (DUR-928:Placebo) ratio:

- DUR-928:150 mg [PPD/CCI] on Day 1 and on Day 4
- Placebo: Sterile Water for Injection [PPD/CCI] on Day 1 and on Day 4

Above study treatments will be diluted in [REDACTED] and administered at [REDACTED] for approximately 2 hours or until the bag is empty.

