9.4.1 Safety analyses

Treatment emergent SAEs will be listed and summarized. All SAEs reported in this study will be coded using the current Medical Dictionary for Regulatory Activities (MedDRA).

Particular attention will be given to assessment of treatment emergent SAEs in the domains of respiratory failure events, liver events, and renal events.

The overall incidences of SAEs in each system organ class (SOC) and preferred term (PT) will be tabulated. In addition, incidences rates (frequencies and percentages) will be broken down by severity and/or relationship to study drug. Treatment emergent changes from baseline in clinical laboratory tests, ECG, and vital signs will be derived by treatment group.

Safety will be evaluated by assessment of serious adverse events, clinical laboratory tests, and vital signs, starting at Screening.

Status and severity of comorbid conditions such as diabetes (e.g. last known HbA1C, medications), cardiac disease (e.g. previous MI, Stroke, echocardiogram, 12 lead EKG, baseline troponin, WHO heart failure definition), and immunocompromised status will be documented.

Data regarding the use of experimental anti-viral therapies will be collected.

Data on other supportive measures, such as proning, received by subjects who are on invasive mechanical ventilation will be collected.

For subject deaths, data will be collected on whether the death occurred after withdrawal of care and, if so, the reason for withdrawal of care.

For each subject, the reason for hospital admission, the standard of care followed for each subject/site, and if care decisions are made based on resource limitation will all be document.

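### Cheap improvement, not an error: pre-specify the primary test as a Cochran-Mantel-Haenszel test stratified by ventilation status before randomisation

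*Combined protocol and SAP*

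**What the plan says.** - **Primary test.** Section 9.2, and the synopsis under Power Calculations: "A Pearson chi-square statistic will be used to compare the proportion of responders between treatment groups for the primary endpoint". The text that follows in both places is redacted.
- **Randomisation.** Section 5.1.1: "Subjects will be assigned randomly at a 3:1 ratio to the following treatment groups". Section 9.3: "A total of 80 subjects will be enrolled into the following 2 study treatment groups in a 3:1 (DUR-928:Placebo) ratio". Neither names a stratification factor in the readable text, and neither describes the randomisation method. The 3:1 ratio gives 60 and 20 subjects.
- **Eligibility.** Inclusion criterion 3 (section 3.11.1) admits ventilated subjects, with a limit of under 5 days: "If the subject is on ventilator at the time of Day 1 dosing". Exclusion criterion 1 (section 3.11.2) mirrors it: "On mechanical ventilator for" 5 days or more. Subjects who are not ventilated are also eligible.
- **Endpoint.** One of the four components in section 3.9 is "Free of mechanical ventilation at Day 28".
- **Wording.** Section 9.4.1 collects data on supportive measures "received by subjects who are on invasive mechanical ventilation will be collected". The terms therefore run from ventilator, to mechanical ventilator, to mechanical ventilation, to invasive mechanical ventilation. The readable text does not say whether these are the same thing.
- **Aim.** Section 9.1 opens: "While this trial will provide important exploratory analyses of efficacy". Section 9.4 describes the trial's purpose as screening.

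**The concern.** A subject who is ventilated at entry and stays so until Day 28 fails the primary endpoint by definition. Ventilation at entry is therefore plausibly a strong predictor of response, although the documents give neither the ventilated share nor its effect on outcome.

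With about 20 placebo subjects, chance can easily put noticeably more or fewer ventilated subjects in that arm. An unstratified test cannot separate such an imbalance from a drug effect. It also gives up some power when the factor is strongly prognostic and the drug effect is large. An adjustment chosen after unblinding would be open to challenge; one written beforehand would not.

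**Working it through.** **Inputs from the documents.** 80 subjects at 3:1, that is 60 versus 20; Pearson chi-square on responder proportions; ventilated and non-ventilated subjects both eligible.

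**Inputs assumed.** The alpha, response rates and effect size behind the figure of 80 are not readable, so the plan's sample size cannot be reproduced. I assume two-sided 0.05, no dropout, simple allocation with fixed arm sizes, and 10% to 40% ventilated. The central case is 30% ventilated, with placebo response 40% if ventilated and 85% if not. That gives 0.30 × 0.40 + 0.70 × 0.85 = 71.5% on placebo overall.

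**Statistics compared.** Pearson is the uncorrected chi-square on the pooled 2×2 table. The Cochran-Mantel-Haenszel (CMH) statistic without continuity correction is [Σ(x₁ − n₁m/N)]² / Σ[n₁n₀m(N − m)/(N²(N − 1))]. Sums run over the two ventilation strata; x₁ is responders on drug, n₁ and n₀ the arm sizes, m total responders and N the stratum size.

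**Step 1: how often the arms differ (exact).** Ventilated counts are Binomial(60, p) and Binomial(20, p).

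| Ventilated | Gap above 15 points | No ventilated placebo subject, (1 − p)²⁰ | 3 or fewer ventilated on placebo |
|---|---|---|---|
| 10% | 3.9% | 12.2% | 87% |
| 20% | 12.4% | 1.2% | 41% |
| 30% | 18.1% | 0.1% | 11% |
| 40% | 21.2% | 0.0% | 2% |

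**Step 2: false positives with no drug effect (central case, simulation).** Overall, Pearson rejects in 5.0% of trials and CMH in 4.9%. In the 18% of trials with a gap above 15 points, Pearson rejects in about 10.7% and CMH in about 4.9%. In the rest, Pearson rejects in 3.8%. The parts add up: 0.181 × 10.7 + 0.819 × 3.8 = 5.0%.

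**Step 3: power, same odds ratio (OR) in both strata (central case).**

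| OR | Pearson | CMH | Change, points |
|---|---|---|---|
| 1.5 | 9.8% | 10.2% | +0.4 |
| 2 | 17.3% | 19.0% | +1.7 |
| 3 | 31.8% | 36.8% | +5.0 |
| 4 | 44.2% | 50.6% | +6.4 |

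Across 36 strongly prognostic scenarios (10% to 40% ventilated; placebo response 30% to 50% if ventilated, 70% to 90% if not), the change runs from −0.5 to +3.0 points at OR 2 and from +1.1 to +9.3 at OR 4.

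**Step 4: where the gain shrinks or reverses.**
- Moderate prognosis (60% versus 80%), OR 4, 10% to 40% ventilated: about +0.4 to +2.3 points.
- Not prognostic (same response in both strata): −1.4 to +1.0 points. The largest loss is 73.7% to 72.3%, at OR 4, 30% ventilated and 50% response.
- Effect only in ventilated subjects (placebo 40% versus 85%; OR 3 to 6 in that stratum): about −0.9 to 0 points. A harsher case (placebo 30% versus 80%, ventilated response raised to 60%, 20% ventilated) gives −1.3.
- Effect only in non-ventilated subjects (80% raised to 95%, ventilated 30% in both arms; 20% to 50% ventilated): +4.1 to +10.5 points.

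**Step 5: continuity correction.** In the central null case a continuity-corrected CMH rejects only 2.1% of the time. Across the 36 scenarios at OR 1.5 to 4 its power is 4 to 14 points below Pearson's.

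**The case against.** The strongest reply is that nothing is broken. Pearson is valid under randomisation, the trial is a screening study whose efficacy analyses are called exploratory, and the plan gives no reason to single out ventilation over pressor use, kidney injury, liver injury or oxygenation. All of this stands, except that ventilation differs from those features in one respect: its persistence to Day 28 is itself endpoint failure.

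A reader might infer more than the documents support:

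- *That Pearson inflates the false-positive rate.* It does not overall. The excess in imbalanced trials is offset in the others.
- *That the plan has no adjusted analysis and no stratified randomisation.* This cannot be known. Text beside the test sentence and under the hypotheses is redacted, section 9.7 refers to a SAP, and the randomisation method is not described. The point covers only the named primary test and the readable randomisation text.
- *That stratifying always adds power when ventilation matters.* It needs strong prognosis and an effect not confined to ventilated subjects (step 4).

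Two practical objections also stand and shape the fix. Inclusion criterion 3 refers to status at Day 1 dosing, while the Day 1 procedures list randomisation before dosing, so a proper baseline stratum must be tied to a time before randomisation. And the readable screening and Day 1 lists do not name ventilation status as a recorded item. The eligibility check implies that it is known, not that it is in the database.

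**Conclusion.** The point holds as a suggestion to consider, not as an error. Its main value is protection: a chance difference in ventilation between 60 and 20 subjects would no longer distort the primary comparison. The power gain is secondary and conditional: about 2 points at OR 2 and 6 at OR 4 with strong prognosis and a common odds ratio, about 0 to 2 with moderate prognosis, and slightly negative otherwise. It does not rescue a small trial. In the central case power is still 19% at OR 2 and 51% at OR 4 after the change.

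Every rate, effect size and ventilated share here is an assumption, as is two-sided 0.05. If few subjects are ventilated at entry, both the imbalance problem and the benefit become small.

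**What to change.** Before unblinding, in section 9.2, the synopsis and the SAP:

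1. Give one definition of mechanical ventilation and use it for both the endpoint and the stratum. This is worth doing whatever test is chosen.
2. Make the primary test a CMH test without continuity correction, stratified by ventilation status (yes/no) at the last assessment before randomisation.
3. Confirm that this status is recorded on the CRF.
4. Report the Mantel-Haenszel risk difference with its 95% confidence interval.
5. Keep the Pearson test as a sensitivity analysis.
6. State that a stratum with no subject in one arm contributes nothing to the test.

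Stratified randomisation is not required; in the central case it adds under 1 point of power to CMH at OR 1.5 to 4. If it is used, Pearson should not stay primary, because its type I error then falls to 2.9% in the central case.

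The cost is a definition, a few sentences and possibly one CRF item, with no extra patients. The downsides are a loss of up to about 1.5 points of power if ventilation is not prognostic, about 1 point if the drug works only in ventilated subjects, and thin or empty strata if few are ventilated. If the redacted text or the SAP already specifies an adjusted primary analysis, the test needs no change.
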